Evidence suggests that culturally-tailored interventions may increase cessation in AIs but face-to-face delivery is costly and hindered by lack of transportation among participants. Prior work by the American Indian Cancer Foundation (AICAF; subcontract on proposal), shows that references to traditional tobacco in cessation messages can positively affect self-efficacy to quit (unpublished data). To our knowledge, only two culturally-tailored cessation interventions for AI peoples exist that purposely engage AI voices throughout the research and utilized rigorous methodology (i.e., included a control group, biochemically confirmed abstinence). The first is the All Nations Breath of Life (ANBL) intervention which was created for AIs representing many tribes and included pharmacotherapy, in-person behavioral support led by AI facilitators, and culturally-tailored curriculum.¹⁰ Biochemically confirmed abstinence was higher in the tailored versus standard group, though the difference between the groups was not statistically significant (11% vs 7%).¹⁰ The second, a tribal-specific program which included pharmacotherapy, also observed higher, but non-significant, abstinence in the tailored versus standard group (23% vs 14%).¹¹ Both studies observed poor retention (~40% loss-to-follow-up) and lack of transportation was a major contributor. Innovative approaches that can reach AI smokers and, that overcome the barrier of travel to an intervention site are needed to address commercial smoking among AI people.

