3.0 Study Endpoints/Events/Outcomes

3.1 Primary Endpoint/Event/Outcome:

The primary endpoint, which was used for power and sample size is the frequency of app use during the 5-week period.

3.2 Secondary Endpoint(s)/Event(s)/Outcome(s):

Secondary endpoints:

- Frequency of app use during the 1st week post-randomization
- Frequency of interactions with various app features (e.g. quit tips, trigger list) over the 5 weeks
- Study accrual relative to recruitment goal
- Study attrition measured as percentage of randomized participants that complete the survey at 5 weeks
- Frequency of returning saliva sample by 2 weeks post the week 5 survey (i.e., 7 weeks post randomization)
- Following measures at 5 weeks via exit survey
 - Usability of App Design measured using System Usability scale (SUS)³⁴ Acceptability of overall app (i.e., how likely would you be to recommend the app) and various app components (e.g. quit tips, trigger list) measured as Likert-scale responses

Fit of app with culture measured as Likert-scale responses

Exploratory endpoints:

Following measures at 5 weeks via exit survey

- Number of 24-hour quit attempts over the over the 5 week period
- Self-reported 24-hour abstinence at time of exit survey
- Self-reported 7-day abstinence at time of exit survey
- Self-reported 30-day abstinence at time of exit survey
- Nicotine replacement therapy and pharmacotherapy (e.g. Chantix) use over the 5 week period
- Other behavioral support (e.g. in-person, quitline) for smoking cessation over the 5 week period

MEDICAL PROTOCOL (HRP-590)

PROTOCOL TITLE: QuitGuide for American Indians: Aims 2 & 3

VERSION DATE: 11-16-2022

- Saliva cotinine at 5 weeks for those with 7-day abstinence prior to this time point to biochemically confirm self-reported 7-day abstinence (saliva cotinine < 10 ng/mL)

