15.0 Statistical Considerations

15.1 Data Analysis Plan:

No blinding of the investigative team will occur.

General Approach

All statistical analyses will be performed using SAS (version 9.4) or R (latest version, R Core Team). All statistical tests will be two-sided and a significance level of 0.05 will be used. Proper transformation such as the logarithm transformation will be used to approximate normality for

MEDICAL PROTOCOL (HRP-590)

PROTOCOL TITLE: QuitGuide for American Indians: Aims 2 & 3

VERSION DATE: 11-16-2022

the outcome variables. All analyses will be completed using intent-to-treat principle unless otherwise noted.

Describing the Study Population

Baseline characteristics will be summarized for all participants and by study arm to identify any treatment group imbalances post-randomization. This will include household income, education level, traditional tobacco use, cultural identity, multiple tobacco use, quit readiness, nicotine dependence and CPD. Continuous variables will be summarized using mean, standard deviation, median and range, and compared between study arms using Student's t-tests or Wilcoxon rank-sum tests, as appropriate. Categorical variables will be summarized using frequency and percentage, and compared between study arms using Chi-square or Fisher's exact tests, as appropriate.

Primary Endpoint Analysis

The primary endpoint is the frequency of app use initiated by the participant. The number of times the app is initiated per day will be measured using data from Smokefree.gov. If a participant does not use the app on a particular day, Smokefree.gov records this as non-use or 0 for that day. The total number of times will be summarized for analysis by totaling the number of times the app is initiated from randomization to 5 weeks post-randomization.

Primary Analysis

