The objective of our primary analysis is to test the treatment effect on frequency of app initiated by the participant. Frequency of app initiated will be summarized by treatment group (tailored app vs standard app) using descriptive statistics, and analyzed using a Poisson regression model with covariates for treatment group and the three stratification factors (rural/urban clinic, male/female gender and <50 years of age/50+ years of age). Assumptions about mean and variance will be evaluated and if over-dispersion is present, negative binomial regression will be used. If data are zero-inflated, zero-inflated Poisson or negative binomial models may be considered.. This analysis will be performed using data for all participants who were randomized, while assuming non-use of app for those who did not complete the week 5 survey from the last day they launched the app.

Secondary Analysis

A secondary analysis of the primary endpoint will be performed that also adjusts for any other covariates that differ across treatment groups at baseline with a p-value less than 0.20 (covariates listed above). We acknowledge the limitations of this due to a small sample size and will take this into account when determining what additional covariates to adjust for. Additionally, a sensitivity analysis will be performed for all subjects who completed the week 5 survey.

Secondary and Exploratory Endpoint Analysis

Secondary and exploratory endpoints will be analyzed using the same approach as the primary endpoint. These endpoints will be analyzed using an appropriate regression framework (i.e. linear, logistic, Poisson etc.), adjusting only for baseline measurements of the endpoint, if available, and the three stratification factors (rural/urban clinic, male/female gender and <50 years of age/50+ years of age). Secondary analyses will consist of an adjusted analysis, as

MEDICAL PROTOCOL (HRP-590)

PROTOCOL TITLE: QuitGuide for American Indians: Aims 2 & 3

VERSION DATE: 11-16-2022

described above. All analyses will utilize residual plots and other diagnostic statistics to evaluate all modeling assumptions.

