Measures of the ability to abstain from smoking (self-reported 24-hour, 7-day and 30-day abstinence) will be analyzed using a similar approach to the primary and secondary/exploratory endpoints, and summarized using a binary endpoint. Continuous 7-day biochemically-verified abstinence (saliva cotinine < 10 ng/mL⁸) will be summarized for those who self-reported 7-day abstinence prior to the week 5 survey, and analyzed using logistic regression, with a main effect for treatment group and adjustment of the stratification factors (rural/urban clinic, male/female gender and <50 years of age/50+ years of age). Because traditional tobacco (depending on the method of use and plants used) and secondhand smoke can increase saliva cotinine, additional analyses may be performed to explore their impact on biochemically-confirmed abstinence. In addition, secondary analyses will consist of an adjusted analysis, as described in above.

Subgroup Analysis

No subgroup analyses will be performed due to small sample size.

Missing Data

An intent-to-treat analysis requires that subjects are analyzed according to their randomized treatment assignment, regardless of compliance to the study product, and that complete data are available on all study subjects. Every effort will be made to limit the amount of missing data in this trial, and study participants will be incentivized to partake in each study component, return the saliva sample, and complete all components.

We will compare subjects with and without missing data in order to identify baseline covariates associated with missing data. All observed data will be utilized in the analyses, with missing data being assumed to be missing at random. Sensitivity analyses of the secondary/exploratory endpoints using multiple imputation may be considered depending on the amount of missingness.

Interim Analyses

No planned interim analyses.

All statistical analyses will be performed by [name] from the Masonic Cancer Center, Biostatistics Core.

15.2 Power Analysis:

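### The population for the cotinine-verified abstinence model is not settled: one natural reading fits it only among participants who report abstinence, while other sentences point to all randomised

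*Combined protocol and SAP*

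**What the plan says.** Section 15.1 (Secondary and Exploratory Endpoint Analysis) states that verified 7-day abstinence, with saliva cotinine below 10 ng/mL, "will be summarized for those who self-reported 7-day abstinence prior to the week 5 survey, and analyzed using logistic regression". The model has a treatment term and the three stratification factors. Section 3.2 lists the measure as exploratory: "Saliva cotinine at 5 weeks for those with 7-day abstinence prior to this time point to biochemically confirm self-reported 7-day abstinence". That says whose saliva serves for confirmation; it does not set a regression denominator.

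Three other sentences in section 15.1 bear on the population:

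- General Approach: "All analyses will be completed using intent-to-treat principle unless otherwise noted".
- Secondary and Exploratory Endpoint Analysis: "Secondary and exploratory endpoints will be analyzed using the same approach as the primary endpoint". The primary analysis is "performed using data for all participants who were randomized, while assuming non-use of app for those who did not complete the week 5 survey".
- Subgroup Analysis: "No subgroup analyses will be performed due to small sample size".

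On missing values, the Missing Data paragraph gives a general rule, with "missing data being assumed to be missing at random", and leaves multiple imputation as an option. The one rule for week 5 non-completers concerns app use. Nothing says how an unanswered exit survey or an unreturned saliva sample is classified for verified abstinence.

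**The concern.** In the key sentence one subject, verified abstinence, governs both verbs, and claimers are the only group mentioned. The intent-to-treat default yields wherever something else is noted, and this sentence can be taken as such a note. A statistician following it literally would fit the model among claimers.

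That would break the randomised comparison. Membership of the subset depends on a post-randomisation outcome that the app is meant to change, and the odds ratio would compare confirmation among claimers, not verified quitting by arm. A tailored app that doubled both claims and verified quits would show no effect.

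Verified abstinence is the only biochemical measure behind the preliminary-efficacy part of the purpose in section 1.1. The investigative team is not blinded, so the dataset should be fixed before outcomes are seen.

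**Working it through.** **The plan's own figure.** Section 15.2 sizes the trial on app use only: rates 35 and 35 + 3.15 = 38.15, two-sided alpha 0.05, 80% power. n per arm = (1.960 + 0.842)² × (35 + 38.15) / 3.15² = 57.86, rounded up to 58, or 116 in total. This reproduces and is not affected by the point. No sample size or power is given for verified abstinence.

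**Assumptions.** The documents give no claim, confirmation or return rates for this trial, so those below are assumed. For context, section 2.2 cites an 8% self-reported quit rate with QuitGuide. Section 2.3 cites abstinence of 11% vs 7% and 23% vs 14% in two earlier culturally tailored trials that included pharmacotherapy.

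**Odds ratio under each denominator (tailored vs standard).**

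- Claims 20% vs 10%, 70% confirmed in both arms. Verified: 0.20 × 0.70 = 14% and 0.10 × 0.70 = 7%. All randomised: (0.14/0.86)/(0.07/0.93) = 2.16. Claimers only: (0.70/0.30)/(0.70/0.30) = 1.0.
- Verified 11% vs 7%, equal confirmation. All randomised: (0.11/0.89)/(0.07/0.93) = 1.64. Claimers only: 1.0.
- Claims 16% vs 8%, confirmation 40% vs 60%. Verified: 6.4% and 4.8%. All randomised: (0.064/0.936)/(0.048/0.952) = 1.36. Claimers only: (0.40/0.60)/(0.60/0.40) = 0.44, a reversal.

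**Crude direction, first scenario, 58 per arm, exact enumeration.** Claimers only: favours tailored 46.8%, standard 49.2%, tie 3.7%, undefined 0.2%. All randomised: favours tailored 86.3%, standard 8.0%.

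**Sparseness of the adjusted model.** It has five parameters: intercept, arm and three binary factors. At 8% claims in both arms it would rest on 2 × 58 × 0.08 = 9.3 claimers. At 20% vs 10% it would rest on 11.6 + 5.8 = 17.4, of whom 17.4 × 0.30 = 5.2 are unconfirmed. The simulations used 58 per arm, roughly even factors with no effect, full saliva return and 70% confirmation. Approximate shares of trials:

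| Scenario | Claimers only: any coefficient non-finite | Claimers only: arm OR non-finite | Claimers only: arm direction undetermined | All randomised: any coefficient non-finite |
|---|---|---|---|---|
| Claims 20% vs 10% | 48% | 37-39% | 5% | 2.5% |
| Verified 11% vs 7% | 57-59% | 44% | 8% | 3% |
| Verified 23% vs 14% | 8% | 4% | 0.1% | 0.1% |

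At 20% vs 10% claims, the share with any non-finite coefficient runs from about 31-33% at 50% confirmation to about 89-91% at 90%.

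**Power with all randomised, 58 per arm, exact enumeration.** 14% vs 7%: Fisher 14%, chi-square 23%. 16% vs 8%: Fisher 17%, chi-square 26%.

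**Missing samples.** Suppose no true effect (10% claims and 70% confirmed in both arms, so 7% vs 7%) and returns of 80% vs 60%.

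- Missing counted as not verified: 5.6% vs 4.2%, OR (0.056/0.944)/(0.042/0.958) = 1.35.
- Claimers without a sample dropped: 0.056/0.98 = 5.71% vs 0.042/0.96 = 4.38%, OR 1.32.
- Imputed conditional on arm and claim: 7% vs 7%, OR 1.0.

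If claimers without a sample are in fact smoking, the imputed result is the biased one.

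**The case against.** The best counter-argument is grammatical. The Primary Analysis paragraph has the same shape: a summary by arm, then a Poisson model. There the phrase after the first verb limits only the summary. Read likewise, the restriction to claimers here governs only the description, and the model takes the default population. The three sentences listed above support that. This stands as a plausible reading, and it is why a reader should not infer that the plan has settled on a wrong estimand. It does not remove the conflict, because the restriction is still the only population stated for this endpoint.

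A second tempting inference is that the claimers-only model would usually say nothing about the arms. The 48% figure does not show that: it counts trials in which any coefficient separates, including a stratification factor. The arm odds ratio is affected less often, and its direction is seldom undetermined.

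It is also fair that the 1.0 follows from assuming equal confirmation. That assumption illustrates the problem; it does not predict this trial's result.

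Finally, missing data are not ignored. A general missing-at-random rule exists, participants with and without missing data will be compared, and saliva return is already a secondary endpoint. A dedicated rule is therefore added detail, and each candidate rule carries its own bias.

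**Conclusion.** The concern holds as a conflict in the text with one harmful reading. If the model is fitted among claimers, it does not estimate the effect of the tailored app on verified quitting, and its odds ratio is 1.0 whenever confirmation is equal in both arms, whatever the difference in quitting. The adjusted fit would also often be fragile, to a degree that depends strongly on the assumed claim and confirmation rates; at 23% vs 14% verified with full return it is mostly estimable.

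The consequence is limited. The endpoint is exploratory, the stated hypotheses concern feasibility and acceptability, and self-reported abstinence carries no such restriction. Power is about 14-26% for a doubling from 7-8% even with all randomised, so neither denominator would support a firm efficacy conclusion. The missing-data part is secondary. This should be fixed, with medium confidence, since the sponsor may always have meant all randomised.

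**What to change.** State in section 15.1 that the logistic regression for verified abstinence includes all randomised participants. Define success as self-reported 7-day abstinence together with saliva cotinine below 10 ng/mL, and count participants who report smoking as not verified. Keep the adjustment for the three stratification factors, with a sparse-data method such as Firth's if needed. In the simulations Firth made the all-randomised model estimable in every trial. It does not repair the claimers-only estimand: with claims of 20% vs 10% the median odds ratio was 1.03 among claimers and 2.08 with all randomised. Report confirmation among claimers descriptively only.

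As a secondary suggestion, say in advance how unanswered surveys and unreturned samples are classified in the main analysis, and report saliva return by arm beside the result. The choice of rule is the sponsor's. A sensitivity analysis under a different rule would show how far the result depends on it.

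The cost is wording. Saliva kits are already mailed at week 4 and return is already recorded. The change corrects what is estimated; it adds no power.

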8.0 Study Population

8.1 Inclusion Criteria:

- American Indian person based on self-report
- Age \geq 18 years
- Interested in quitting smoking
- Smoke \geq 3 commercial tobacco cigarette per day (CPD) in the past 30 days
 - Use of other commercial tobacco products (e.g., e-cigarettes) is permitted if they report cigarettes being their primary product
- Smartphone ownership with the ability to download applications and sufficient data to complete research procedures

8.2 Exclusion Criteria:

- New or change in pharmacotherapy for smoking cessation (includes: nicotine gum, patch, lozenge, inhaler OR medications Chantix/Wellbutrin/Zyban/Bupropion) in past month

MEDICAL PROTOCOL (HRP-590)

PROTOCOL TITLE: QuitGuide for American Indians: Aims 2 & 3

VERSION DATE: 11-16-2022

- Does not speak or read English

8.3 Screening:

Individuals are screened for eligibility by undergoing a phone screening interview with a research coordinator. The screening consists of questions about eligibility criteria. Participants who are eligible can then complete informed consent and enroll into the study—see informed consent section.

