13.0 Risks to Participants

13.1 Foreseeable Risks:

The potential risks of this study are minimal and include the risks associated with the loss of confidentiality, boredom of participating, and adverse psychological events from smoking reduction/cessation due to nicotine withdrawal.

Nicotine withdrawal symptoms include sadness, difficulty sleeping, irritability, restlessness, anxiousness and are usually mild and fade with time. These symptoms present among smokers who quit in the real-world—not just exclusive to our study. The QuitGuide app has existing links to a 24-hour crisis center and information for participants to get help shall they need it as well as information on treatments (e.g., nicotine replacement therapy) to help reduce nicotine withdrawal. These resources will be maintained in the tailored version of the app. Nicotine withdrawal symptoms will be captured at the exit survey as part of an exploratory outcome via the Minnesota Nicotine Withdrawal Scale but will not be considered adverse events for this study.

Measures collected will be noninvasive and should present no psychological or medical risk to the participant. Participants will be told that they may refuse to answer any questions during baseline and follow-up surveys and they may decide to quit their participation at any time.

13.2 Reproduction Risks:

No risks to reproduction are expected with this study.

13.3 Risks to Others:

No risks to others are expected with this study.

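### The cotinine rule for verified smoking abstinence makes no provision for nicotine-replacement users, and the plan does not say how vaping counts

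*Combined protocol and SAP*

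**What the plan says.** Section 3.2 lists, among the exploratory endpoints, "Saliva cotinine at 5 weeks for those with 7-day abstinence prior to this time point", collected "to biochemically confirm self-reported 7-day abstinence (saliva cotinine < 10 ng/mL"). Section 15.1 treats this as one of the "Measures of the ability to abstain from smoking (self-reported 24-hour, 7-day and 30-day abstinence" and related endpoints, and analyses the verified version by logistic regression on arm and the stratification factors. The outcome is binary. The text does not say in words that a value of 10 ng/mL or more is a failure, but that follows from the definition.

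Section 15.1 then gives a caveat: "Because traditional tobacco (depending on the method of use and plants used) and secondhand smoke can increase saliva cotinine", analyses of the impact of those two sources may be done. They are optional, and no other source is named.

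Elsewhere the protocol allows or expects other nicotine sources:

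- Section 8.2 excludes only "New or change in pharmacotherapy for smoking cessation (includes: nicotine gum, patch, lozenge, inhaler" and the listed medications) in the past month, so stable use is admitted.
- Section 3.2 makes "Nicotine replacement therapy and pharmacotherapy (e.g. Chantix) use over the 5 week period" an exploratory endpoint.
- Section 13.1 says the app contains "information on treatments (e.g., nicotine replacement therapy) to help reduce nicotine withdrawal" and that this content stays in the tailored version.
- Section 8.1 says: "Use of other commercial tobacco products (e.g., e-cigarettes) is permitted if they report cigarettes being their primary product".

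**The concern.** The condition to be verified is not smoking; the assay measures exposure to nicotine. The two agree only in people who take no nicotine from elsewhere. Someone who stops cigarettes with the help of a patch, gum, lozenge or inhaler is abstinent in the sense of section 15.1, yet is likely to fail the cotinine test. The plan recognises this mechanism for traditional tobacco and secondhand smoke but not for nicotine replacement, which it admits, records and describes to participants.

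What is at stake is the reading of the only biochemically verified cessation result in a trial whose stated purpose (section 1.1) includes preliminary efficacy. Verified abstinence would tend to be understated, and a reader could not tell a participant who went back to smoking from one who quit using nicotine replacement.

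**Working it through.** **Plan's own figure.** The one calculated figure in section 15 is the sample size. With rates 35 and 35 + 3.15 = 38.15, two-sided alpha 0.05 and 80% power, n per arm = (1.960 + 0.842)² × (35 + 38.15) / 3.15² = 57.86, rounded up to 58. It reproduces. Abstinence does not enter it, so this point leaves it unchanged.

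**Nicotine sources set side by side.**

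| Source | At entry | During the 5 weeks | Listed in exit survey (5.2) | Named in 15.1 caveat |
|---|---|---|---|---|
| Traditional tobacco | allowed | not restricted | not listed (baseline only) | yes |
| Secondhand smoke | allowed | not restricted | not listed (baseline only) | yes |
| Nicotine replacement | allowed if not new or changed in past month | not restricted; an endpoint | yes, under pharmacotherapy | no |
| E-cigarettes | allowed if cigarettes are the primary product | not restricted | not listed | no |

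No section gives nicotine-replacement or e-cigarette users an exemption, another biomarker, another cutoff or a sensitivity analysis. Section 15.1 lists multiple tobacco use as a baseline covariate. It enters the adjusted analysis only if the arms differ at p < 0.20, and covariate adjustment does not correct a misclassified outcome.

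**How many people.** Inputs: 116 randomised (section 15.2); 8% quit rate, not biochemically verified, from the earlier QuitGuide testing in section 2.2. Carrying that rate over to 7-day abstinence at 5 weeks is an assumption. The share of abstainers using a nicotine product is not in the documents; 10% to 50% is assumed.

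- Self-reported abstainers: 0.08 × 116 = 9.3.
- Affected if all return saliva: 0.10 × 9.3 = 0.9 to 0.50 × 9.3 = 4.6, so about 1 to 5.
- If only 60% return saliva (assumed): 0.60 × 9.3 = 5.6 samples, of which 0.6 to 2.8 are affected.

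These counts treat every user as reaching 10 ng/mL, so they are upper figures for each assumed share.

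**Effect on the rates.** Verified rate = true rate × (1 − share of abstainers using a nicotine product). For illustration, take the 11% and 7% of the first prior trial in section 2.3 as true rates, with 58 per arm.

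| Share tailored / standard (assumed) | Verified tailored | Verified standard | Difference (points) |
|---|---|---|---|
| 0 / 0 | 11.0% | 7.0% | 4.0 |
| 20% / 20% | 8.8% | 5.6% | 3.2 |
| 40% / 40% | 6.6% | 4.2% | 2.4 |
| 40% / 20% | 6.6% | 5.6% | 1.0 |
| 20% / 40% | 8.8% | 4.2% | 4.6 |

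Equal shares shrink the difference in proportion. Unequal shares move it either way. With 20% in the standard arm, the order would reverse only if the tailored share exceeded 1 − 0.056/0.11 = 49%. In people, the gap is 0.11 × 58 − 0.07 × 58 = 6.4 − 4.1 = 2.3. Power for 11% against 7% at 58 per arm is about 11% even with no misclassification.

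**The case against.** The best counter-argument is that the endpoint is exploratory in a feasibility trial sized on app use, and that self-reported 24-hour, 7-day and 30-day abstinence are analysed by arm anyway. A reader will see the unverified 7-day result beside the verified one. That stands and limits the importance of the point. It does not remove it, because the gap between the two results would mix false reports, unreturned samples and genuine quitters on nicotine replacement.

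Two stronger readings are tempting, and the documents do not support either.

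- *Vapers are wrongly failed.* The definitions page counts vaping liquid as commercial tobacco, and section 2.1 frames the need as quitting commercial tobacco. On that view, someone who gives up cigarettes but vapes nicotine has not succeeded. Section 15.1 speaks of smoking. The construct is ambiguous, so failing vapers is not plainly an error. Permission at entry does not settle what counts as success at week 5.
- *The app that prompts more medication use will look worse, perhaps reversing the comparison.* This needs different nicotine-replacement uptake by arm. Section 13.1 says the existing information is kept in the tailored app, and the list of app changes mentioned in section 4.1 is not among the documents. Because nicotine-replacement use is an endpoint, an imbalance would be visible. With so few events, chance alone could also reverse the order.

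Three qualifications are accepted. The analyses named in section 15.1 are optional and do not form a closed list. The exit-survey contents are given only as headings, so the absence of an e-cigarette item is not established. The point does not apply to varenicline, bupropion or nicotine-free liquid.

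**Conclusion.** The point holds for nicotine replacement: followed as written, the rule is likely to classify smoking-abstinent users as not abstinent, and nothing in the plan deals with them. For e-cigarettes, the finding is only that the plan does not say whether vaping counts as abstinence.

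The number affected is unknown. About 1 to 5 people out of roughly 9 self-reported abstainers is an illustration. It rests on the borrowed 8% rate, an assumed 10% to 50% share, full saliva return and cotinine at or above the cutoff in every user. The documents do not state that nicotine replacement raises cotinine; this follows from cotinine being a nicotine metabolite. The direction and size of any between-arm bias cannot be determined. This is an inexpensive improvement to one exploratory endpoint, not a flaw in the trial's main comparison.

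**What to change.** 1. In section 15.1, add use of nicotine-containing replacement in the 7 days before the sample to the named cotinine sources, taken from the pharmacotherapy data in the exit survey. Check that the survey item allows that window to be identified.
2. Report verified abstinence by arm under the stated rule. Report it again with self-reported abstainers who use nicotine replacement flagged as not verifiable by cotinine and classified by self-report. Show the number flagged in each arm, and label the second version as partly unverified.
3. State whether vaping counts as abstinence, reconciling the wording of section 15.1 with the definitions page. If it does, make sure the exit survey records current e-cigarette use, and show those participants as a separate row.

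Cost: a sentence or two in the analysis plan, possibly one survey item, and one extra table. No new assay is needed. The downside is that the second version rests on self-report for a few people, which is why the stated rule should still be reported alongside it.
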